### ***Bone Marrow Aspiration and/or Biopsy***

A bone marrow aspirate (and biopsy if necessary) is mandatory and must be obtained within 28 days prior to enrollment to obtain a current estimate of the % plasma cells in the marrow. Analysis for % plasma cells in the marrow will be performed locally. After screening, a bone marrow aspirate (or biopsy if necessary) must be performed to document a CR response and may otherwise be repeated as clinically indicated at the discretion of the treating physician.

Subjects who provide informed consent for biomarker assessments will have samples collected and processed as per separate lab manual. Bone marrow aspirate material will be collected during the mandatory bone marrow assessment at screening and during other bone marrow assessments that are clinically indicated (Confirmation of CR, and at disease progression).

### ***Extramedullary Plasmacytoma Assessments***

Extramedullary plasmacytoma assessments/measurements at specified time-points are only required if extramedullary plasmacytomas (EMPs) are present.

If EMPs are clinically assessable, clinical assessment will be performed at screening, at every Cycle Day 1, and at treatment discontinuation.

If EMPs are only assessable radiographically (x-ray and/or conventional [spiral] CT/MRI [computed tomography/magnetic resonance imaging] scan), scans are required at screening, at Cycle 3 Day 1, every 3 cycles thereafter (Cycle 6 Day 1, Cycle 9 Day 1, etc.) during treatment, at treatment discontinuation, and when clinically indicated to confirm a response  $\geq$  PR. All scans will be reviewed locally only.

### ***Skeletal Survey***

A skeletal survey by x-ray will be performed at screening and when clinically indicated per the investigator's discretion. If a skeletal survey was performed within 60 days prior to the start of Cycle 1 as part of standard medical care, it may be used for the screening assessment. All skeletal survey films will be performed and analyzed locally by the site investigator/radiologist. The x-rays will not be collected for centralized review. Refer to [Appendix C](#) for detailed requirements.

### ***Assessment of Response***

Response, including PD, will be assessed using the mIMWG criteria ([Appendix B](#)) at Day 1 of each Cycle and at the treatment discontinuation visit.

### ***Overall Survival and Subsequent Anti-MM Therapies***

During the follow-up period, survival status and subsequent therapies for MM must be collected and entered into the eCRF. All subjects will be assessed 4 times a year (every 3 months) to determine survival status for up to 5 years after the last subject is enrolled in each respective cohort. Primary cause of death (medical condition) is to be recorded in the eCRF and the subject's medical record. All subsequent therapies given for MM must be collected and entered into the eCRF.

### ***Exploratory Biomarker Study***

Normal tissue (saliva), whole blood, and bone marrow aspirate material at defined time-points or events will be taken from subjects who give informed consent in Cohort A and all subjects in Cohort B at clinical sites that are able to collect and process the mandated samples. Only non-invasive approaches to collect normal tissue for comparative analysis with tumor specimens will be used. Samples will be collected and processed as per separate lab manuals.

The bone marrow aspirate will be collected at screening during the mandatory screening procedure and at other times on study when clinically indicated. All samples will be destroyed 5 years after completion of the study or earlier if required by law.

Samples to be collected:

- Excess bone marrow aspirate will be collected from the procedure mandated for study entry and also collected at other time points as response assessment or treatment discontinuation when clinically indicated for Cohort A and Cohort B. For Cohort C, bone marrow aspirate will be collected at screening and treatment discontinuation.
- For Cohort A and Cohort B, whole blood sample will be collected at screening, at time of response and/or at treatment discontinuation (disease progression) when a bone marrow procedure is being performed. Additionally, whole blood will be collected Day 1 of Cycle 3 and 5 for Cohort A and Cycle 1 Day 1, Cycle 1 Day 8, Cycle 1 Day 15, Cycle 2 Day 1, Cycle 2 Day 15, Cycle 3 Day 1, and Cycle 5 Day 1 for Cohort B.
- Normal tissue: Saliva samples collected at screening by noninvasive methods for Cohort A and Cohort B.

Bone marrow aspirates and cellular fractions isolated from them will be used for nucleic acid (eg, gene expression profiling and DNA sequencing), protein, and other biochemical analyses. These studies will focus on genomes, candidate genes, proteins, and signaling pathways identified by earlier work and will characterize aberrations associated with high-risk MM and changes induced by pomalidomide or pomalidomide/daratumumab based therapy. Serially collected samples may be used to study changes associated with clonal evolution and for measuring depth of responses to therapy. The analytical techniques involved will include methods such as cell sorting, immunohistochemistry, flow cytometry, Western blotting techniques, array-based and Quantitative polymerase chain reaction (QPCR) gene expression profiling, DNA sequencing and allele copy number measurements. The CD 138 + and CD 138- cells isolated from bone marrow mononuclear cells will be used for DNA, gene expression, and protein analysis. Analyses of DNA for subsets of genes and specific dysregulated pathways associated with pomalidomide/dexamethasone or pomalidomide/daratumumab/dexamethasone

activity or genetic aberrations associated with high-risk multiple myeloma will be evaluated for mutations, aberrations, or changes in copy number (ie, allelic loss or gain). Gene expression analyses will be conducted from baseline as well as subsequent samples for comparison of pomalidomide/dexamethasone or pomalidomide/daratumumab/dexamethasone treatment effect on the expression of genes, such as cereblon. Similarly, for proteins, targets (such as Cereblon, IRF 4, cMyc, etc) and other factors important for pomalidomide/daratumumab/dexamethasone synergistic activity will be measured by several techniques such as immunohistochemistry, western analysis or flow cytometry respectively. In some subjects, clonal evolution of MM cells or minimal residual disease (MRD) may be measured using bone marrow aspirates collected at diagnosis to study depth of response to pomalidomide, daratumumab and LD-dex and the sensitivity of different subclones of the MM disease to treatment by using sensitive next generation sequencing-based approaches.

### ***Quality of Life (QoL)***

For subjects enrolled in Cohort B, Quality of Life (QoL) as measured by the descriptive system of the EQ-5D will be provided to each subject to complete on Day 1 of every cycle prior to any study treatment (POM, DARA, LD-Dex) administration and at treatment discontinuation. See [Appendix I](#) for EQ-5D questionnaire to be used.

## 7. STUDY POPULATION

### 7.1. Number of Subjects and Sites

This is a multicenter, multi-cohort, open label, phase 2 study of POM + LD-dex or POM+DARA+LD-dex in adult subjects with relapsed or refractory MM.

This study is anticipated to enroll approximately 188 subjects with relapsed MM or refractory MM who fulfill the eligibility criteria. At the time of this amendment #4, enrollment to Cohort A and B already completed with 56 and 112 subjects respectively. Cohort C will enroll approximately 20 subjects in Japan.

### 7.2. Inclusion Criteria

Subjects must satisfy the following criteria to be enrolled in the study:

1. Adults (age  $\geq 18$  years at the time of signing the ICD) with documented diagnosis of MM and measurable disease (serum M-protein  $\geq 0.5$  g/dL or urine M-protein  $\geq 200$  mg/24 hours).
2. Subjects enrolling in Cohort A (POM+LD-dex) must have received 2 prior treatment lines of anti-myeloma therapy. Subjects enrolling in Cohort B and Cohort C (POM+DARA+LD-dex) must have received 1 or 2 prior treatment lines of anti-myeloma therapy.
3. All subjects must have received prior treatment with LEN or a LEN-containing regimen for at least 2 consecutive cycles as the most recent treatment regimen.
4. All subjects must have documented disease progression during or after their last anti-myeloma therapy.
5. Subjects must have an Eastern Cooperative Oncology Group (ECOG) performance status score of 0, 1, or 2.
6. Subjects must understand and voluntarily sign an ICD prior to any study related assessments/procedures being conducted.
7. Subjects must be able to adhere to the study visit schedule and other protocol requirements.
8. All subjects must provide an adequate bone marrow sample at screening that definitively evaluates the presence or absence of myelodysplastic changes.
9. Females with child-bearing potential (FCBP†) must agree to use 2 reliable forms of contraception\* simultaneously or practice complete abstinence from heterosexual contact for at least 28 days before starting study drug, while participating in the study (including

---

† This protocol defines a female of childbearing potential as a female who: 1) has achieved menarche at some point, 2) has not undergone a hysterectomy or bilateral oophorectomy, or 3) has not been naturally postmenopausal (amenorrhea following cancer therapy does not rule out childbearing potential) for at least 24 consecutive months (ie, has had menses at any time in the preceding 24 consecutive months).

\* The two methods of birth control used may be selected from the following categories, but the two methods cannot be selected from any one category: barrier method: ie, condom (male or female) or diaphragm with spermicide; hormonal: eg, contraceptive pill, patch; intrauterine device (IUD); vasectomy; or tubal ligation.

during dose interruptions), and for at least 28 days after study treatment discontinuation and must agree to regular pregnancy testing during this timeframe. For subjects enrolled in Cohort B and Cohort C, pregnancy prevention and testing will continue until 3 months after last dose of daratumumab.

10. Females must agree to abstain from breastfeeding during study participation and 28 days after study drug discontinuation. Female subjects enrolled in Cohort B and Cohort C must agree to abstain from breastfeeding and donating eggs during study participation and until 3 months after last dose of daratumumab.
11. Males must agree to use a latex condom during any sexual contact with FCBP while participating in the study and for 28 days following discontinuation from this study, even if he has undergone a successful vasectomy. Male subjects enrolled in Cohort B and Cohort C must agree to use a latex condom during any sexual contact with FCBP while participating in the study and until 3 months after last dose of daratumumab.
12. Males must also agree to refrain from donating semen or sperm during the treatment phase and for 28 days after discontinuation from this study treatment. Male subjects enrolled in Cohort B and Cohort C must also agree to refrain from donating semen or sperm during the treatment phase and until 3 months after last dose of daratumumab.
13. All subjects must agree to refrain from donating blood while on study therapy and for 28 days after discontinuation from this study treatment.
14. All subjects must agree not to share medication.

### 7.3. Exclusion Criteria

The presence of any of the following will exclude a subject from study enrollment:

1. Any of the following laboratory abnormalities:
  - Absolute neutrophil count < 1,000/ $\mu$ L
  - Platelet count < 75,000/ $\mu$ L for subjects in whom < 50% of bone marrow nucleated cells are plasma cells; or a platelet count < 30,000/ $\mu$ L for subjects in whom  $\geq$  50% of bone marrow nucleated cells are plasma cells.
  - Severe renal impairment (Creatinine Clearance [CrCl] < 30 mL/min) requiring dialysis.
  - Corrected serum calcium > 11.5 mg/dL (> 2.8 mmol/L)
  - Hemoglobin < 8 g/dL (< 4.9 mmol/L; prior red blood cell transfusion or recombinant human erythropoietin use is permitted)
  - Serum SGOT/AST or SGPT/ALT > 3.0 x the upper limit of normal (ULN)
  - Serum total bilirubin > 2.0 mg/dL (34.2  $\mu$ mol/L); or > 3.0 x ULN for subjects with hereditary benign hyperbilirubinemia
2. Prior history of malignancies, other than MM, unless the subject has been free of the disease for more than 5 years. Allowed exceptions include the following:
  - Basal or squamous cell carcinoma of the skin

- Carcinoma in situ of the cervix or breast
  - Incidental histological finding of prostate cancer (TNM [tumor, nodes, metastasis] stage of T1a or T1b)
3. Previous therapy with pomalidomide or daratumumab
  4. Hypersensitivity to thalidomide, LEN, or dex (this includes  $\geq$  Grade 3 rash during prior thalidomide or LEN therapy)
  5. Subjects who received an allogeneic bone marrow or allogeneic peripheral blood stem cell transplant less than 12 months prior to initiation of study treatment and who have not discontinued immunosuppressive treatment for at least 4 weeks prior to initiation of study treatment and are currently dependent on such treatment.
  6. Subjects with any one of the following:
    - Congestive heart failure (NY Heart Association Class III or IV)
    - Myocardial infarction within 12 months prior to starting study treatment
    - Unstable or poorly controlled angina pectoris, including Prinzmetal's variant angina pectoris
  7. Subjects who received any of the following within 14 days of initiation of study treatment:
    - Major surgery (kyphoplasty is not considered major surgery)
    - Use of any anti-myeloma drug therapy
  8. Use of any investigational agents including for the treatment of multiple myeloma within 28 days or 5 half-lives (whichever is longer) of treatment, unless approved by the sponsor.
  9. Incidence of gastrointestinal disease that may significantly alter the oral absorption of Pomalidomide.
  10. Subjects unable or unwilling to undergo antithrombotic prophylactic treatment
  11. Any serious medical condition, laboratory abnormality, or psychiatric illness that would preclude participation in the study, or interfere with interpretation of the study results
  12. Pregnant or breastfeeding females
  13. Known human immunodeficiency virus (HIV) positivity; active infectious hepatitis A, B, or C; or chronic hepatitis B or C.

All subjects will be tested for hepatitis B surface antigen (HBsAg), hepatitis B surface antibody (antiHBs), and hepatitis B core antibody (antiHBc). Subjects with the following serological testing are considered not eligible:

- HBsAg positive
- HBsAg negative, anti-HBs positive and/or anti-HBc positive and detectable viral DNA

Note:

- Subjects who are HBsAg negative, anti-HBs positive, and/or anti-HBc positive, viral DNA negative are eligible. For these subjects, DNA monitoring and prophylactic medication for HBV reactivation are recommended per local practice.
- Subjects who are seropositive because of hepatitis B virus vaccination are eligible (anti-HBs positive, anti-HBc negative, and HBsAg negative).

All subjects will be tested for hepatitis C antibody. Subjects are not eligible if known seropositive for hepatitis C virus.

Note:

- Subjects who are hepatitis C antibody positive but show no detectable viral RNA for 6 months prior to initiation of study treatment are eligible.

14. For subjects enrolling in Cohort B and Cohort C - Subject has known allergies, hypersensitivity to mannitol, corticosteroids, monoclonal antibodies or human proteins, or their excipients (refer to the Daratumumab IB), or known sensitivity to mammalian-derived products.

## **8. DESCRIPTION OF STUDY TREATMENTS**

### **8.1. Description of Investigational Product(s)**

Pomalidomide will be supplied as Investigational Product by Celgene Corporation as 1 mg, 2 mg, 3 mg, and 4 mg capsules for oral administration. Investigational product will be packaged in bottles containing a 21-day supply of POM.

Daratumumab will be supplied as Investigational Product by Celgene Corporation in single-use vials in single-count cartons. Daratumumab is a colorless to pale yellow, preservative-free solution and will be supplied in as 400 mg/20 mL or 100 mg/5 mL vials for intravenous administration. For Cohort C, 400 mg/20 mL vials for intravenous administration will be supplied. For reconstitution, administration and storage after reconstitution information, please refer to the pharmacy manual.

Dexamethasone for oral administration is approved and commercially available for patients with MM. Investigative sites will use commercial oral dex for this study, which will be provided to subjects via prescription. For Cohort C, dexamethasone will be supplied as 2 mg or 4 mg tablets for oral administration as Investigational Product by Celgene Corporation. This protocol only contains summary information on dex administration, the full product information and labeling contained in the current dex Package Insert should be reviewed prior to administration.

Other recommended/required concomitant medications per the protocol such as aspirin (or other antithrombotic or anti-coagulants), antihistamines, antipyretics (or other medications administered for infusion of DARA) and growth factors are commercially available and will be provided at the site by investigator(s) prescription. Celgene will not provide these medications.

### **8.2. Treatment Administration and Schedule**

All study drug doses will be administered orally or intravenously, and subjects will be instructed about the dosing schedules for the study.

Subjects enrolled in Cohort A of this study will receive:

- Oral POM at the starting dose of 4 mg/day on Days 1-21 of a 28-day cycle
- Oral LD-dex at the starting dose of 40 mg/day ( $\leq$  75 years old) or 20 mg/day ( $>$  75 years old) on Days 1, 8, 15, and 22 of a 28-day cycle.

Subjects enrolled in Cohort B and Cohort C of this study will receive:

- Oral POM at the starting dose of 4 mg/day on Days 1-21 of a 28-day cycle
- Oral LD-dex at the starting dose of 40 mg/day ( $\leq$  75 years old) or 20 mg/day ( $>$  75 years old) on Days 1, 8, 15, and 22 of a 28-day cycle.
- DARA administered intravenously at a starting dose of 16 mg/kg at following schedule:
  - Days 1, 8, 15, and 22 of a 28-day cycle for Cycle 1 and Cycle 2
  - Days 1 and 15 for Cycle 3 through Cycle 6
  - Day 1 for Cycle 7 and each cycle thereafter until disease progression

Subjects will also be instructed to return the study drug bottles (and any remaining study drug) at the next visit for drug accountability purposes. For FCBP, study drug will not be dispensed until the investigator has verified that the results of the pregnancy test are negative. Females of childbearing potential other than the subject should not handle study drug unless wearing gloves.

All subjects enrolled into the study will continue study treatment until progressive disease or unacceptable toxicity, death, withdrawal of active participation in the study or withdrawal of consent, or lost to follow-up, or as long as they benefit from therapy according to the opinion of the responsible study investigator.

### Dose Modification and Interruption

Dosing interruptions and reductions are permitted throughout the study.

In the event of any dose reduction for POM, site staff must contact the Interactive Voice Response System (IVRS) to record the new dose level.

If the treatment has been interrupted and the next cycle is delayed beyond 28 days after Day 1 of the prior cycle, then Day 1 of the next cycle will be defined as the first day that treatment is resumed.

Subjects will be evaluated for AEs at each visit with the NCI-CTCAE (version 4.03) as a guide for the grading of severity.

- If POM is permanently discontinued, then the subject must be permanently discontinued from all study treatments.
- For Patients in Cohort B and Cohort C, if DARA is withheld or permanently discontinued, then POM, and LD-Dex dosing may be continued.
- If LD-dex dosing is withheld or permanently discontinued, then POM and DARA (for patients in Cohort B and Cohort C) dosing may be continued.

### Dose Modification Instructions for Pomalidomide

Detailed instructions for POM dose interruptions and reductions are provided in [Table 2](#). [Table 3](#) outlines the dose reduction steps for POM.

If POM administration is withheld, LD-dex should also be withheld.

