**Table 2: Dose Modification Instructions for Pomalidomide**

Toxicity a	Dose Modification
Neutropenia Grade 4 neutropenia (ANC < 500/ $\mu$ L) or Febrile neutropenia (ANC < 1,000/ $\mu$ L with a single temperature of > 38.5 °C or a sustained temperature of $\geq$ 38 °C for more than one hour)	Withhold the dose and follow CBC weekly. If the subject was not receiving GCSF therapy, GCSF therapy may be started at the discretion of the treating physician. When dosing is resumed, the dose of POM may be maintained if neutropenia was the only POM-related toxicity requiring a dose modification and GCSF treatments are continued. Otherwise, decrease by one dose level. Note, ANC must be $\geq$ 500/ $\mu$ L to restart dosing For Cohort C, ANC must be $\geq$ 1000/ $\mu$ L to restart dosing
Thrombocytopenia Grade 4 thrombocytopenia (Platelets < 25,000/ $\mu$ L)	Withhold the dose and follow CBC weekly. Dosing may resume at one dose level lower once the platelet count has recovered to $\geq$ 50,000/ $\mu$ L.

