**Table 2: Dose Modification Instructions for Pomalidomide (Continued)**

Toxicity	Dose Modification
Rash, Grade 3	Withhold dose for remainder of cycle. Decrease by one dose level when dosing restarted at next cycle (rash must resolve to $\leq$ Grade 1 before restarting dosing).
Rash, Grade 4 or Blistering	Discontinue subject from study treatment.
VTE $\geq$ Grade 3	Withhold dose for remainder of cycle. Assess anticoagulation treatment. Maintain dose level when dosing restarted at next cycle at discretion of treating physician.
Other $\geq$ Grade 3 POM-related b adverse events	Withhold dose. Decrease by one dose level when dosing restarted (adverse event must resolve to $\leq$ Grade 2 before restarting dosing).

ANC = absolute neutrophil count; GCSF = granulocyte colony-stimulating factor; POM = pomalidomide; VTE = venous thromboembolism.

a If recovery from toxicities is prolonged beyond 14 days, then the dose of POM will be decreased by one dose level when dosing is restarted.

b For Grade 3 or 4 AEs that are not considered to be related to study drug, the treating physician should consult with the sponsor for dose interruptions and reductions.

To initiate a new cycle of POM, the neutrophil count must be  $\geq 500/\mu\text{L}$  and for Cohort C, the neutrophil count must be  $\geq 1000/\mu\text{L}$  with or without granulocyte colony-stimulating factor (GCSF), the platelet count must be  $\geq 50,000/\mu\text{L}$ , and non-hematologic AEs must have recovered as outlined in [Table 2](#).

If recovery from toxicities is prolonged beyond 14 days, then the dose of POM will be decreased by one dose level when dosing is restarted. Prior to restarting treatment after a prolonged delay, subjects should be assessed to ensure they have not developed progressive disease.

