### Daratumumab Dose Modifications

For infusion reactions of any grade/severity, immediately interrupt the DARA infusion and manage symptoms. Management of infusion reactions may further require reduction in the rate of infusion, or treatment discontinuation of DARA as outlined below ([Table 6](#)).

- Grade 1-2 (mild to moderate): Once reaction symptoms resolve, resume the infusion at no more than half the rate at which the reaction occurred. If the patient does not experience any further reaction symptoms, infusion rate escalation may resume at increments and intervals as appropriate ([Table 6](#)).
- Grade 3 (severe): If the intensity of the reaction decreases to Grade 2 or lower, consider restarting the infusion at no more than half the rate at which the reaction occurred. If the patient does not experience additional symptoms, resume infusion rate escalation at increments and intervals as outlined in [Table 6](#). Repeat the procedure above in the event of recurrence of Grade 3 symptoms. Permanently discontinue DARA upon the third occurrence of a Grade 3 or greater infusion reaction.
- Grade 4 (life threatening): Permanently discontinue DARA treatment.

During a cycle, a daratumumab dose must be held if any of the following criteria below are met, to allow for recovery from toxicity. The criteria for a dose delay are:

- Grade 4 hematologic toxicity, or Grade 3 or higher thrombocytopenia with bleeding;
- Febrile neutropenia of any grade;
- Neutropenia with infection, of any grade;

- Grade 3 or higher nonhematologic toxicities with the following exceptions:
  - Grade 3 nausea or Grade 3 vomiting that responds to antiemetic treatment,
  - Grade 3 diarrhea that responds to antidiarrheal treatment,
  - Isolated Grade 3 Gamma-glutamyltransferase elevation
  - Grade 3 fatigue or asthenia that was present at baseline or that lasts for < 7 days after the last administration of daratumumab

If daratumumab administration does not commence within the prespecified window (Table 6) of the scheduled administration date, then the dose will be considered a missed dose.

Administration may resume at the next planned dosing date.

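### In Cohorts B and C the plan does not say whether dexamethasone is still given before a daratumumab infusion while pomalidomide is on hold

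*Combined protocol and SAP*

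**What the plan says.** Section 8.2 (Dose Modification Instructions for Pomalidomide) states: "If POM administration is withheld, LD-dex should also be withheld". The sentence is not limited to Cohort A.

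Table 2 sets the pomalidomide holds:

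- Grade 4 thrombocytopenia: "Withhold the dose and follow CBC weekly. Dosing may resume at one dose level lower once the platelet count has recovered to"; the level set is at least 50,000/µL.
- Grade 4 or febrile neutropenia: restart at an ANC of 500/µL, but 1000/µL in Cohort C.
- Grade 3 rash: "Withhold dose for remainder of cycle. Decrease by one dose level when dosing restarted at next cycle (rash must resolve to"; the level set is Grade 1 or lower.
- VTE of Grade 3 or higher: "Withhold dose for remainder of cycle. Assess anticoagulation treatment".
- Other pomalidomide-related events of Grade 3 or higher: "Withhold dose. Decrease by one dose level when dosing restarted (adverse event must resolve to"; the level set is Grade 2 or lower.

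Section 8.3 (Daratumumab Dose Modifications) has a separate list: "During a cycle, a daratumumab dose must be held if any of the following criteria below are met, to allow for recovery from toxicity". It covers Grade 4 hematologic toxicity, Grade 3 or higher thrombocytopenia with bleeding, febrile neutropenia, neutropenia with infection, and Grade 3 or higher non-hematologic toxicity with named exceptions. A pomalidomide hold is not a criterion.

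Section 8.3 (Pre-infusion Medication) tells sites to premedicate all subjects about an hour before each daratumumab infusion. The first item is the protocol dose of oral dexamethasone. The Infusion Reactions text in the same section again lists corticosteroids. Section 8.2 (Dose Modification and Interruption) lets daratumumab continue while dexamethasone is withheld.

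**The concern.** The dexamethasone rule in Section 8.2 makes no provision for a second drug whose premedication is that same dexamethasone dose. If pomalidomide is off and daratumumab is due, one section withholds the dose and the other calls for it. A site can omit the steroid, give dexamethasone against the hold, or delay the infusion.

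Each choice has a cost. Omission removes the named steroid from an antibody infusion. Giving the dose departs from Section 8.2. Delay is costly because the note to Table 6 says that missed doses are not made up and that a toxicity hold of more than 14 days ends daratumumab for good. About 20 Cohort C subjects are to be enrolled under this text, and that cohort has the higher ANC restart level. What is at stake is subject safety and consistent dosing.

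**Working it through.** The plan gives no figure on this point, so there is nothing to reproduce. The check has two steps.

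**Step 1: can pomalidomide be on hold when no daratumumab criterion is met?** Table 2 is set against the Section 8.3 list.

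| State | Pomalidomide (Table 2) | Daratumumab (Section 8.3) | Cohorts |
|---|---|---|---|
| 1. Pomalidomide-related isolated Grade 3 GGT elevation; Grade 3 nausea, vomiting or diarrhea that responds to treatment; Grade 3 fatigue within the stated exception | Held under the *Other* row | Named exceptions, so no hold even at onset | B, C |
| 2. Platelets 25,000-49,999/µL, no bleeding, after Grade 4 (below 25,000/µL) | Off until 50,000/µL | No longer Grade 4; Grade 3 counts only with bleeding | B, C |
| 3. ANC 500-999/µL, no fever or infection, after Grade 4 (below 500/µL) | Off until 1000/µL | No longer Grade 4 | C only |
| 4. Grade 3 rash, or VTE of Grade 3 or higher, since improved below Grade 3 | Off for the rest of the cycle | Criterion no longer met | B, C |

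State 3 does not arise in Cohort B: its restart level (500/µL) is also the upper limit of Grade 4, so the band is empty. State 1 needs no recovery phase and is the clearest case. In all four states Section 8.2 withholds dexamethasone. If the infusion goes ahead, Section 8.3 calls for it.

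**Step 2: which infusions are exposed?** The schedule is in Section 8.2.

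- Infusions in Cycles 1-6: 4 + 4 + 2 + 2 + 2 + 2 = 16.
- Cycle 1 Day 1 starts treatment, so no hold can precede it: 1 removed.
- Day 1 of Cycles 2-6: 5 removed. When a cycle is delayed, Section 8.2 moves Day 1 to the day treatment resumes. I take that to be the day pomalidomide restarts.
- Mid-cycle infusions: 16 - 1 - 5 = 10.
- On pomalidomide dosing days (Days 1-21): Days 8 and 15 of Cycles 1-2 (2 × 2 = 4) plus Day 15 of Cycles 3-6 (4 × 1 = 4), giving 8.
- On Day 22 of Cycles 1-2, when no pomalidomide is scheduled: 10 - 8 = 2.
- From Cycle 7 daratumumab is given on Day 1 only, so there are no mid-cycle infusions.

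For a rest-of-cycle hold (rash or VTE), the most infusions one subject could have left are:

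| Hold starts | On pomalidomide days | Including Day 22 |
|---|---|---|
| Cycle 1 or 2, Days 2-7 | 2 | 3 |
| Cycle 1 or 2, Days 8-14 | 1 | 2 |
| Cycle 1 or 2, Days 15-21 | 0 | 1 |
| Cycles 3-6, before Day 15 | 1 | 1 |

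These are upper limits, because infusions due before the event falls below Grade 3 are themselves held. The documents give no rate for any of the four states, so no count of subjects is derived.

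**The case against.** Four objections carry weight.

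- **The wording is soft on both sides.** Section 8.2 says *should*, and the premedication text sits under a heading of recommended medications. Section 9.3 does refer to these medications as required, but in a sentence about recording them on the eCRF. This stands in part: the premedication text itself is an instruction covering all subjects and every infusion.
- **Steroid cover is possible without LD-dex.** A reader might infer that the plan forces an infusion without a steroid. The documents do not support that. The Infusion Reactions text calls for corticosteroids in general, the Protocol Summary and Section 9.1 permit premedication, and Section 9.2 restricts only chronic steroid use. What remains is that none of these says which rule governs or names a substitute.
- **Daratumumab need not resume as soon as a grade clears.** Section 8.3 frames the hold as time for recovery and gives no recovery count. In states 2-4 an investigator may wait, within the 14-day limit. This stands. It does not apply to state 1, where no daratumumab hold begins.
- **The count can be read too generously.** Pomalidomide is not scheduled on Day 22, so whether it is *withheld* that day is open. The count is therefore 8, with 2 arguable. Also, scheduled on-treatment hematology is on Day 1 only; mid-cycle counts come from the weekly CBCs that Table 2 asks for during a cytopenia hold, or from local testing.

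A reader might also add Grade 3 anemia or leukopenia under the *Other* row. The new-cycle rule in Section 8.2 says "and non-hematologic AEs must have recovered as outlined in" Table 2, which points to a narrower reading of that row, so these events are left out.

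**Conclusion.** The gap is real and minor. Two instructions give different answers for the dexamethasone dose on a daratumumab day during a pomalidomide hold, and no text ranks them. At most 8 of the 16 infusions in Cycles 1-6 are exposed, or 10 if Day 22 is counted, and only in subjects who are in one of the four states when an infusion is due.

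The safety consequence is limited. Section 8.3 says about half of patients react, most of them at the first infusion, which cannot follow a pomalidomide hold; reactions at later infusions remain possible. Cohort B has finished enrolling, so the prospective benefit is clearest for the roughly 20 Cohort C subjects.

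The conclusion rests on reading the daratumumab hold list as complete and on Day 1 of a delayed cycle being the day pomalidomide restarts. It does not bear on the response-rate analysis or any other endpoint analysis.

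**What to change.** After the Section 8.2 sentence on withholding dexamethasone with pomalidomide, add:

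> In Cohorts B and C, if a DARA infusion is given while POM is withheld, corticosteroid pre-infusion medication is still given per Section 8.3 (the protocol dexamethasone dose, or an equivalent corticosteroid if dexamethasone is itself withheld or discontinued under Table 4 and a corticosteroid is not contraindicated).

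This also covers dexamethasone held for its own toxicity during a pomalidomide hold. It leaves the investigator free to hold daratumumab longer. Requiring daratumumab to be held with pomalidomide would be a worse remedy, because it could use up the 14-day limit for a state that meets no daratumumab criterion.

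The cost is one sentence, ideally in place before Cohort C dosing. No threshold, visit, procedure or sample size changes. The downside is that dexamethasone is not spared on those daratumumab days.
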